### **5. TREATMENT PLAN**

#### **5.1 Treatment Regimen**

This is a phase 2 study of treatment with eribulin mesylate +/- pembrolizumab, in metastatic HR-positive breast cancer. Eighty-eight participants will be randomized (1:1) to eribulin mesylate with pembrolizumab (Arm A) or eribulin mesylate (Arm B). Participants randomized to eribulin mesylate monotherapy will have the option to receive pembrolizumab monotherapy at time of progression but they must meet the criteria in section 5.2.3 and begin treatment within 2 months of progression to crossover. Eribulin mesylate will be administered on days 1 and 8 of each 21 day cycle. Pembrolizumab will be administered on day 1 of each 21 day cycle. If treatment is delayed, all protocol required assessments will be delayed accordingly.

Treatment will be administered on an outpatient basis. Reported adverse events and potential risks are described in Section 7. Appropriate dose modifications are described in Section 6. Details of the regimen are described in Table 1/2. No investigational or commercial agents other than those described below may be administered with the intent to treat the participant's malignancy.

Treatment regimen is described in Table 1 (Arm A) and in Table 2 (Arm B).

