- g. For any subject who showed first radiologic evidence of progressive disease (PD) by RECIST 1.1 (see Section 11.1.4) and is deemed clinically stable (see section 5.6), it is at the discretion of the investigator to continue treating the subject until progression is confirmed at least 4 weeks from the date of the first radiologic evidence of PD. If progression is confirmed, the subject will be discontinued from study treatment. Otherwise, the subject will continue treatment and radiographic scans. Any subject who had initial radiologic progression and is deemed clinically unstable should be discontinued from both study drugs and no subsequent scan for confirmation is required.
- h. Tumor assessments should continue as scheduled for participants on Arm B who crossover to receive pembrolizumab.
- i. During follow-up of patients who went off study for reasons other than PD, tumor assessments should continue every 9 to 12 weeks from the date of the last assessment until progressive disease is documented
- j. Optional biopsy should be obtained within 7 days before starting protocol therapy. See Section 9, appendices, and lab manual for biopsy handling and processing instructions.
- k. Optional tumor biopsy should be offered only in patients who go off study for progressive disease. See Section 9, appendices, and lab manual for biopsy handling and processing instructions. For patients randomized for the eribulin mesylate arm who wish to cross over to pembrolizumab arm, a biopsy at progression is mandatory for those whose disease is amenable for biopsy.
- l. 1 block or 20 unstained slides should be collected. If archival tissue is not available, patients with safely accessible disease should have a baseline biopsy.
- m. Off treatment visit is to occur within 30 days of final administration of study treatment. End of treatment assessments do not have to be repeated if the same assessments were performed within 7 days prior to the visit.
- n. Research blood should only be collected on patients who come off treatment for progressive disease.
- o. Optional blood collection for immune cells/cfDNA may be offered to patients who develop progressive disease during follow-up.
- p. Survival status should be collected annually, either by review of the medical record or by phone call (see Section 5.8).

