## 11. MEASUREMENT OF EFFECT

## 11.1 Antitumor Effect – Solid Tumors

Response and progression will be evaluated in this study using the new international criteria proposed by the Response Evaluation Criteria in Solid Tumors (RECIST) guideline (version 1.1) [Eur J Ca 45:228-247, 2009]. Changes in the largest diameter (unidimensional measurement) of the tumor lesions and the shortest diameter in the case of malignant lymph nodes are used in the RECIST criteria.

Pembrolizumab, like other immunotherapeutic agents, may produce antitumor effects by potentiating endogenous cancer-specific immune responses. The response patterns seen with such an approach may extend beyond the typical time course of image responses seen with cytotoxic agents, and can manifest as a clinical response after an initial increase in tumor burden or even the appearance of new lesions.

For any subject who showed first radiologic evidence of progressive disease (PD) by RECIST 1.1 (see Section 11.1) and is deemed clinically stable, it is at the discretion of the investigator to continue treating the subject until progression is confirmed at the next scheduled restaging (or with a confirmatory completed at least 4 weeks from the initial date of PD). If progression is not confirmed on the subsequent scan, the subject should continue to receive treatment and have radiographic scans performed according to the study calendar [approximately every 3 cycles (9 weeks) for the first 12 months and then every 4 cycles (12 weeks)]. If radiologic progression is confirmed, then the subject should be discontinued from all study treatment. If the treating investigator feels that the participant is clinically stable, demonstrates improved condition, or is clearly continuing to benefit from the treatment; the PI may approve the participant to continue to receive study treatment. In all participants, the date of progression will be documented as the first date progression was observed.

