### 11.1.3 Methods for Evaluation of Disease

All measurements should be taken and recorded in metric notation using a ruler, calipers, or a digital measurement tool. All baseline evaluations should be performed as closely as possible to the beginning of treatment and never more than 4 weeks before the beginning of the treatment.

The same method of assessment and the same technique should be used to characterize each identified and reported lesion at baseline and during follow-up. Imaging-based evaluation is preferred to evaluation by clinical examination unless the lesion(s) being followed cannot be imaged but are assessable by clinical exam.

**Clinical lesions.** Clinical lesions will only be considered measurable when they are superficial (*e.g.*, skin nodules and palpable lymph nodes) and  $\geq 10$  mm in diameter as assessed using calipers (*e.g.*, skin nodules). In the case of skin lesions, documentation by color photography, including a ruler to estimate the size of the lesion, is recommended.

**Chest x-ray.** Lesions on chest x-ray are acceptable as measurable lesions when they are clearly defined and surrounded by aerated lung; however, CT is preferable.

**Conventional CT and MRI.** This guideline has defined measurability of lesions on CT scan based on the assumption that CT thickness is 5mm or less. If CT scans have slice thickness greater than 5 mm, the minimum size of a measurable lesion should be twice the slice thickness. MRI is also acceptable in certain situations (*e.g.* for body scans).

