## **13. STATISTICAL CONSIDERATIONS**

### **13.1 Study Design/Endpoints**

This is a randomized phase II open label study of eribulin mesylate +/- Pembrolizumab for patients with metastatic HR positive breast cancer treated with 0-2 line of chemotherapy. Eighty-eight patients will be randomized (1:1) to eribulin mesylate with pembrolizumab or eribulin mesylate. Patients randomized to eribulin mesylate monotherapy will have the option to receive pembrolizumab monotherapy at time of progression.

The primary endpoint is PFS, defined as the time from study randomization to disease progression per RECIST 1.1 or death due to any cause, whichever occurred first. Patients alive without disease progression are censored at the date of last disease evaluation. The primary objective is to compare PFS of patients randomized to receive eribulin mesylate in combination with pembrolizumab (Arm A) versus those randomized to receive eribulin mesylate monotherapy (Arm B).

Secondary endpoints include PFS per irRECIST criteria, ORR per RECIST 1.1 and irRECIST, DOR, CBR, OS, safety and tolerability. For the patients randomized to the eribulin monotherapy arm who elect to receive the combination after progression, we will also perform an exploratory analysis of all clinical endpoints for patients using measurements at progression on monotherapy as the baseline tumor assessment.

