In the group of patients treated with Pembrolizumab after progression on eribulin mesylate, CBR, PFS, OS, and DOOR after they received Pembrolizumab will be estimated using binomial, Kaplan-Meier and descriptive statistics, respectively with 95% confidence intervals. For this group, PFS and OS will start from the time of initiating Pembrolizumab. Under an assumption that approximately two-thirds of patients elect to cross over (n=30), the maximum width to an exact confidence interval for a proportion will be 0.374.

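### The crossover baseline is the scan at progression on eribulin, which can be about 2 months old at the first pembrolizumab dose, so exploratory crossover ORR, CBR and PFS can be biased downward

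*Combined protocol and SAP*

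**What the plan says.** Objective 1.3.6 explores ORR, CBR, DOR and PFS on pembrolizumab after progression on eribulin. Section 13.1 says these crossover endpoints are analysed "using measurements at progression on monotherapy as the baseline tumor assessment".

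Four other provisions bear on how old that baseline can be:

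- Section 5.1 requires crossover patients to "begin treatment within 2 months of progression to crossover".
- Section 11.1 lets a clinically stable patient stay on treatment until progression is confirmed at least 4 weeks later, yet "the date of progression will be documented as the first date progression was observed".
- Section 13.5 states that for the crossover group "PFS and OS will start from the time of initiating Pembrolizumab".
- Section 11.1.3 says baseline evaluations are to be made "never more than 4 weeks before the beginning of the treatment", and calendar footnote f gives the same limit as 28 days.

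Nothing expressly resets the baseline at crossover. The crossover criteria in sections 3.4 and 3.5 ask for no scan. Calendar footnote h says only: "Tumor assessments should continue as scheduled for participants on Arm B who crossover to receive pembrolizumab".

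**The concern.** The size reference and the PFS clock start at different times. Whatever the tumour does between the progression scan and the first pembrolizumab dose is measured as if it happened on pembrolizumab. By then the patient has progressed on eribulin, so the expected direction is growth. Growth in the gap makes progression easier to meet and response harder. An unequivocal new lesion arising in the gap is RECIST progression whatever the target lesions do.

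The effect runs one way and depends on scheduling, so more patients would not remove it. At stake is the reading of a stated secondary objective, the trial's only look at pembrolizumab alone after eribulin.

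**Working it through.** **The plan's own figure.** Section 13.5 expects about 30 crossover patients and a maximum exact interval width of 0.374. Two-thirds of 44 is 29.3. The Clopper-Pearson 95% interval for n = 30 is widest at 15 of 30, from 0.313 to 0.687, a width of 0.374. The figure reproduces, and the baseline definition does not change it: this is a question of bias, not precision.

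**Inputs from the protocol.** Maximum gap 2 months, taken as 61 days (5.1). Baseline limit 28 days (11.1.3, footnote f). Scan interval 9 weeks = 63 days in the first year (footnote f). RECIST PR is a 30% fall from baseline; PD is a 20% rise from the smallest sum, and at least 5 mm (11.1.3.1).

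**Assumptions.** The documents give no growth rate and no distribution of gaps. I assume the sum grows 20% per 63 days (the progression threshold reached in one scan interval) or 20% per 126 days (reached over two), and continues at that rate until the first dose.

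**Formulas.** With gap g and growth period P in days:

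- sum at first dose relative to baseline: R = 1.2^(g/P)
- true shrinkage from first dose needed for PR: 1 - 0.7/R
- further growth from first dose that reaches +20%: 1.2/R - 1

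| Growth assumed | Gap (days) | R | Shrinkage for PR | Further growth to +20% |
|---|---|---|---|---|
| 20% per 63 days | 61 | 1.193 | 41.3% | 0.6% |
| 20% per 126 days | 61 | 1.092 | 35.9% | 9.9% |
| 20% per 63 days | 28 | 1.084 | 35.4% | 10.7% |
| 20% per 126 days | 28 | 1.041 | 32.8% | 15.2% |
| no growth before dosing | any | 1.000 | 30.0% | 20.0% |

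Two limits apply to the last column. Below a baseline sum of 25 mm (5/0.20) the 5 mm rule governs rather than the 20%. Once the sum falls below baseline on pembrolizumab, the nadir becomes the reference and the old baseline no longer affects progression.

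**A second growth model.** If diameter grows by 2^(g/(3T)), with assumed volume doubling times T of 60, 90, 120 and 200 days, growth before dosing is 26.5%, 17.0%, 12.5% and 7.3% over 61 days, against 11.4%, 7.5%, 5.5% and 3.3% over 28 days. A 61-day gap reaches +20% by itself only if T is about 77 days or shorter.

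**irRECIST.** Section 13.1 speaks of all clinical endpoints, and section 11.3 uses products of diameters with a 25% progression threshold. If both diameters grow alike, the product at 61 days is 1.193² = 1.42 (+42%, past the threshold) at the faster rate, and 1.092² = 1.19 (+19%, short of it) at the slower.

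**Confirmed progression.** A patient treated through to a confirmatory scan has a first progression scan at least 28 days old by then. If that first scan is the baseline, it is at or beyond the limit in 11.1.3 when crossover begins, although a newer scan exists.

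**The case against.** The strongest reply is that the text allows milder readings and the stakes are modest.

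- Section 11.1.3 covers all baseline evaluations, so it can be read as limiting 13.1 and requiring a newer scan when the gap exceeds 4 weeks. That stands as a reading. It makes this an unreconciled conflict rather than a settled breach, but no passage says which rule yields.
- Section 13.1 refers to measurements at progression, not to the first progression scan, and 11.1 fixes only the date. A reader might infer that a confirmatory scan must be ignored; the documents do not say so. Nor do they say it is used.
- Footnote h need not mean that scans stay on the eribulin timetable. Footnote f ties scans to cycles rather than weeks, and sections 5.1 and 6 delay assessments with treatment, so counting in crossover cycles is a natural reading. The alternative matters: a scan due 63 days after progression would fall 2 days after a first dose given at day 61.
- The largest figures combine the maximum gap with fast growth. Progression is measured from a nadir that may be several scans back, and progression by new or non-target lesions implies no particular target growth. This stands, and it is why a range is shown.
- The analysis is exploratory, without a comparison between arms, in about 30 patients. This limits the severity. It excuses imprecision more readily than a one-directional bias that can be reduced by wording.

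A reader might also infer that any growth before dosing is scored as pembrolizumab failure. It is not: target growth alone gives RECIST progression only at +20% and 5 mm, and smaller growth only shifts the thresholds.

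**Conclusion.** The point holds as a moderate one. The stated baseline, the 2-month allowance and the PFS start at first dose together permit a reference scan about 61 days old, in conflict with the 4-week window for longer gaps. Growth or new lesions in that interval can count against pembrolizumab, biasing crossover ORR, CBR and PFS downward. Under 20% growth per 9 to 18 weeks and the maximum gap, the sum is about 9-19% above baseline at first dose, and PR needs about 36-41% true shrinkage instead of 30%. The average bias cannot be stated, because gaps and growth rates are unknown; shorter gaps make it smaller.

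It does not follow that the crossover results cannot be read as pembrolizumab activity. The bias works against the drug, so a response seen despite it remains credible; low response or short PFS is what would be hard to interpret. No direction is shown for DOR. Crossover OS, the primary comparison and its power are unaffected.

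**What to change.** - In 13.1 and 13.5, define the crossover baseline as the most recent tumour assessment on or before the first crossover dose, including any confirmatory scan.
- Reconcile 13.1 and 5.1 with 11.1.3 and footnote f by stating whether the 28-day window applies at crossover.
- In footnote h, state that crossover scans are counted in cycles from the first crossover dose.
- Keep all crossover-treated patients in the main ORR, CBR, DOR and PFS estimates. Add a sensitivity analysis restricted to those whose baseline scan was within 28 days of the first dose. Dropping the others from the main response estimates would select on scheduling and depart from the principle in 13.5 and 13.7.1 of evaluating everyone who starts therapy.

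The cost is a few sentences, a little extra analysis, and a smaller n in the sensitivity analysis only. Sample size, power and the 0.374 width for n = 30 do not change. The last-scan definition alone does not help a patient with no scan after the first progression scan; the sensitivity analysis shows how much such patients matter.

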### **13.2 Sample Size, Accrual Rate and Study Duration**

The target accrual is 88 patients (44 in eribulin mesylate alone arm and 44 in eribulin mesylate+pembrolizumab combination arm). The study has 83% power to distinguish a 3 month improvement in PFS from 4.1 to 7.1 months (HR = 0.58) with a one-sided alpha of 0.1. This statement of power assumes a final analysis when 70 PFS events are observed, and would be anticipated to occur after a constant accrual over 18 months with 6 months of additional follow-up. Further assumptions are a constant hazard of PFS and dropout such that 5% of patients are lost-to-follow-up at 1 year. This allows for one futility analysis at 50% information (35 PFS

events) and would stop early if the Z-statistics from the logrank test is less than 0 (i.e. observed HR from a Cox model  $> 1.0$ ).

The expected accrual rate is 3-5 patients per month, and the accrual is expected to complete within 18-24 months.

### **13.3 Interim Monitoring Plan**

A single interim analysis for futility is planned to minimize the likelihood of exposing study patients to an inactive regimen. The interim analysis will be performed at 50% information, when the 44th patient is evaluable for response. Stopping criteria were set considering Lan-Demets (O'Brien Fleming) beta-spending function, and shifting the boundary slightly to  $Z = 0$  (from  $Z = 0.116$ ) to correspond to no observed difference in the proportion of response or worse outcomes with the combination of Eribulin/Pembrolizumab. This boundary corresponds to a Bayesian predicted probability of 3.5% of concluding superiority at final analysis with a non-informative prior of treatment effects. Futility criteria are non-binding, and enrollment will not be suspended for patient follow-up and interim analysis. No early stopping for efficacy will be considered.

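### Sections 13.2 and 13.3 give different triggers for the one futility look, and the 3.5% and Z = 0.116 in 13.3 do not reproduce as described

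*Combined protocol and SAP*

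**What the plan says.** Section 13.2 bases its power statement on 70 PFS events and continues: "This allows for one futility analysis at 50% information (35 PFS" events), where the trial "would stop early if the Z-statistics from the logrank test is less than 0", which it equates with an observed Cox hazard ratio above 1.0. Section 13.4 likewise ties the group sequential methods to the logrank comparison of RECIST 1.1 PFS.

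Section 13.3 also describes one look only, but times it by patients: "The interim analysis will be performed at 50% information, when the 44th patient is evaluable for response". It derives the rule from a Lan-DeMets O'Brien-Fleming "beta-spending function, and shifting the boundary slightly to" Z = 0 from Z = 0.116, and says that Z = 0 corresponds to "no observed difference in the proportion of response or worse outcomes with the combination of Eribulin/Pembrolizumab". It adds: "This boundary corresponds to a Bayesian predicted probability of 3.5% of concluding superiority at final analysis with a non-informative prior of treatment effects". Finally, "Futility criteria are non-binding, and enrollment will not be suspended for patient follow-up and interim analysis".

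Response is a secondary endpoint (13.1). Section 13.5 names a Pearson chi-squared test for the response comparison but does not link it to the interim look.

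**The concern.** Half of 88 patients is not half of 70 PFS events, so the two sections can call for the look at different dates. The 13.3 trigger does not fix the amount of PFS information, because the proportion of patients who count as evaluable for response is left open. Eligibility (3.1.2) asks for an evaluable lesion, whereas 11.1.1 requires measurable disease for target response and has a separate non-target category. The mention of response proportion also blurs which statistic the board should look at, although 13.3 itself names no response test.

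In an open-label trial, two readings of the only formal stopping rule leave its timing, and arguably its endpoint, to be settled after data have accrued. Mislabelling the 3.5% matters in a similar way: a reader who takes it as the predictive probability sees a stop at Z = 0 as better supported than it is.

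**Working it through.** **Inputs (13.2 unless noted).** Medians 4.1 and 7.1 months, 70 final events, one-sided alpha 0.10 (critical Z 1.2816), 88 patients randomized 1:1, 5% lost to follow-up at 1 year, accrual over 18 months for the power statement and 18-24 months in the accrual statement. First scan at 9 weeks, i.e. 2.07 months (Section 10, footnote f). The evaluable share is assumed.

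**1. The stated power.** Drift = (√70/2) × ln(7.1/4.1) = 2.297 (2.279 at the rounded HR 0.58). With continuation if Z1 > 0 at information fraction t = 35/70 = 0.50, and correlation √t between looks:

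- P(Z1 > 0, Z2 > 1.2816) = 83.0% (82.6% at HR 0.58).
- False stop under the design effect = Φ(−2.297 × √0.5) = 5.2% (5.4% at HR 0.58).
- Expected events at 18 + 6 months = 69.9.

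So 83% and 70 events are consistent with the 13.2 rule. A Freedman calculation without a look gives a similar 82.7-83.1%; it too rests on PFS events.

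**2. Where the 13.3 trigger falls.** Look time = 44/share ÷ (88/A) + 2.07 months, with A the accrual period. Expected events use exponential PFS, uniform accrual and the stated dropout, under the design alternative. Power applies logrank Z < 0 at that look.

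| Accrual | Share evaluable | PFS events | Information | Power |
|---|---|---|---|---|
| 18 months | 100% | 25 | 36% | 80.6% |
| 18 months | 90% | 28.7 | 41% | 81.7% |
| 18 months | 77% | 35 | 50% | 83.0% |
| 18 months | 70% | 40 | 57% | 83.7% |
| 24 months | 100% | 27 | 39% | 81.3% |
| 24 months | 90% | 31 | 45% | 82.3% |
| 24 months | 80% | 36.5 | 52% | 83.3% |
| 24 months | 70% | 43 | 62% | 84.0% |

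The 35th event is expected at month 13.7 (18-month accrual) or 16.6 (24-month). The triggers coincide only if about 77% or 83% of patients, respectively, are evaluable. Simulation with actual logrank tests (12,000 trials per setting, 18-month accrual) gave 82.1% power for 13.2, 79.7% for 13.3 at 100% evaluable, and 82.9% at 70%. At 100% evaluable, the 5th-95th percentile of events at the look was 19 to 31.

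**3. The 3.5%.** At Z1 = 0 and t = 0.5:

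- Conditional power under HR = 1: 1 − Φ(1.2816/√0.5) = 1 − Φ(1.812) = 3.5%.
- Flat-prior predictive probability: 1 − Φ((1.2816 − Z1/√t)/√((1−t)/t)) = 1 − Φ(1.2816) = 10.0%.
- A flat-prior value of 3.5% would need Z1 = −0.375, an observed HR of exp(0.375 × 2/√35) = 1.14.

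The match with conditional power holds for any one-sided 0.10 test, so it does not reveal which endpoint was meant.

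**4. The boundary 0.116.** With type II error β = 0.17, spending at t = 0.5 is 2 − 2Φ(z(1−β/2)/√0.5) = 0.0523. The boundary is Φ⁻¹(0.0523) + 2.297 × √0.5 = 0.00 (−0.01 at HR 0.58). Reaching 0.116 at the same drift needs β of 19.3-19.6%. Using 0.116 instead of 0 would give power 82.4% and false stop 6.6%.

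**5. If response was really meant (illustration only).** Take 22 per arm, control response rate 11% (the eribulin rate quoted in Section 2.4) and combination rates of 11, 16, 21, 26 and 31%. The combination rates are assumptions; the documents give none. The exact binomial chance that the combination is strictly worse is 40, 24, 13, 6 and 3%. If a tie also stops, it is 60, 40, 24, 13 and 7%.

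**The case against.** The strongest reply is that the two sections agree on what matters: one look, 50% information, a boundary at Z = 0, futility only. Sections 13.2 and 13.4 name the logrank test and 13.3 names no other, so the conflict may be no more than a wrong trigger phrase and a stray reference to response. That is fair for the statistic, where the wording blurs rather than plainly contradicts. It does not remove the conflict in timing.

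The size of the timing effect also rests on assumption. No section gives an evaluable share, and 11.1.1 does make patients with non-measurable disease evaluable in the non-target category. Counting evaluability later shrinks the gap at 100% evaluable: at 3 months, 28.5 events and 81.6% power with 18-month accrual, or 30.1 events and 82.0% with 24-month. The 2.4-point loss is the worst case in the grid.

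For 0.116, Section 13.3 states no type II error or drift, so the test borrows those of 13.2. Solving power and boundary together, 0.116 would need a type II error of about 21.7% instead of 19.3-19.6%. What stands is that the figure cannot be obtained from the stated design; it is a query to the trial statistician rather than a proven error. It has no operating role, since Z = 0 is the boundary in force.

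Finally, Section 12.2 does not list the 3.5% among the items that the board may receive. Relabelling it moves no boundary.

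**Conclusion.** The concern holds. The trigger conflict is explicit in the text and nothing resolves it. The 13.3 trigger corresponds to roughly 25 to 43 PFS events against the 35 in 13.2, given a 9-week evaluability point and an assumed evaluable share of 100% down to 70%. As a matter of timing alone, power changes from a loss of about 2.4 points to a gain of about 1. Read as a response comparison, 13.3 gives no response rates or test from which power could be derived.

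The 3.5% is conditional power under no effect; the quantity that 13.3 names is 10.0%, taking a non-informative prior as flat on the log hazard ratio. The 0.116 does not follow from 13.2's design, which gives about 0.00.

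The consequences are bounded. The rule is non-binding, so power is lost only if a stop is obeyed. Type I error is not inflated, the final test is unchanged, and the monitoring board reviews toxicity and response twice a year (12.2). The point should be fixed because this is the plan's only formal stopping rule.

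**What to change.** Rewrite 13.3 to match 13.2: one non-binding futility look when 35 RECIST 1.1 PFS events have occurred in the primary-analysis population, stopping if the logrank Z is below 0 (Cox HR of Arm A to Arm B above 1). Remove the trigger based on response-evaluable patients and the reference to response proportion. Whether the population is ITT (13.4) or modified ITT (13.7.1) is a separate question that this wording does not settle.

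Relabel the 3.5% as conditional power under HR = 1, or replace it with the predictive probability of about 10.0%. Recheck the 0.116 and state the type II error and drift behind it. If a response-based look was intended, state instead the evaluable set, the assumed response rate in each arm and the test, and restate the power.

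The cost is a wording amendment and one recalculation. Under the design alternative, the 35-event look falls with about 67 patients enrolled (18-month accrual) or 61 (24-month). Over the same evaluable range, that is between 2.6 months later and 1.2 months earlier than the 13.3 trigger (54 to 73 enrolled) with 18-month accrual, and between 2.5 months later and 2.6 months earlier (52 to 70 enrolled) with 24-month accrual.

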### **13.4 Analysis of Primary Endpoints**

The primary analysis of the study will be the comparison of PFS per RECIST 1.1 between Arm A and Arm B using logrank test and group sequential methods to control the overall one-sided Type I error rate at 0.1.

The null and alternative hypotheses are defined using the hazard ratio (HR) of the Arm A to Arm B as:

$$\begin{aligned} H_0: & \text{ HR} \leq 1 \\ H_1: & \text{ HR} > 1 \end{aligned}$$

All inferences will be conducted in the intent-to-treat manner, and the survival function will be summarized using the Kaplan-Meier methods according to randomized treatment assignment. Final analysis will be performed after 70 PFS events are observed or at least 12 months after the last patient is enrolled on study, whichever occurs first.

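### The 3.5% Bayesian predictive probability quoted for the Z = 0 futility boundary is 10.0% on the plan's own inputs; 3.5% is what conditional power at HR = 1 gives.

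*Combined protocol and SAP*

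**What the plan says.** Section 13.2 sets the design. The test is made "with a one-sided alpha of 0.1", and on the final event count it says: "This statement of power assumes a final analysis when 70 PFS events are observed". One futility look is planned at half the information, after 35 PFS events, and the trial "would stop" condition is a logrank Z below 0, which the section equates with an observed Cox hazard ratio above 1.

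Section 13.3 explains the boundary. It starts from a Lan-DeMets O'Brien-Fleming beta-spending function and moves the resulting value from 0.116 to 0, so that it corresponds to no observed difference. It then adds: "This boundary corresponds to a Bayesian predicted probability of 3.5% of concluding superiority at final analysis with a non-informative prior of treatment effects". It makes the futility rule non-binding and rules out the other kind of early stop: "No early stopping for efficacy will be considered".

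Section 13.4 says the PFS comparison will use "group sequential methods to control the overall one-sided Type I error rate at 0.1".

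**The concern.** A predictive probability under a non-informative prior allows for uncertainty about the treatment effect. At half the information that uncertainty is large, so the final Z can move a long way from an interim value of 0. A figure as low as 3.5%, against a one-sided alpha of 0.1, looks like a calculation in which the effect was held fixed.

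The figure matters because it is the only chance-of-success number the plan gives for its only interim rule. The rule is non-binding, so a result near the boundary calls for judgement. Those making it would read that a trial at the boundary has about a 1 in 29 chance of success (1/0.035), when the stated method gives 1 in 10. Anyone who computed the predictive probability as described would get 10% at the boundary and appear to contradict the plan.

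**Working it through.** **Inputs, all from the documents**

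- One-sided alpha 0.1 (13.2, 13.4).
- 70 final PFS events, and a look at 35, so t = 0.5 (13.2; 13.3 also says 50% information).
- Interim boundary Z = 0, with positive Z favouring the combination (13.2, 13.3).
- Non-binding futility and no efficacy stopping (13.3). No alpha is spent or recovered at the interim, so the final critical value is c = z(0.90) = 1.2816.
- Non-informative prior on the treatment effect (13.3), taken as flat on the log hazard ratio.

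**Step 1: reproduce the plan's power.** With HR = 4.1/7.1 = 0.5775, the drift at 70 events is −ln(0.5775) × √70/2 = 2.297.

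- Without the futility stop: Φ(2.297 − 1.2816) = 84.5%.
- With a stop at Z < 0 after 35 events (bivariate normal, correlation √0.5): 83.0%, which is the plan's figure.
- With the rounded HR of 0.58: 84.1% and 82.6%.

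The inputs are therefore the ones behind the plan's own power statement.

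**Step 2: predictive probability at the boundary.** With a flat prior,

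PP = 1 − Φ[(c − Z/√t) / √((1 − t)/t)].

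At Z = 0 and t = 0.5 the denominator is √(0.5/0.5) = 1, so PP = 1 − Φ(1.2816) = **10.0%**. Monte Carlo with 4 million draws gives 10.01%.

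**Step 3: what does give 3.5%.** Conditional power with HR fixed at 1 is

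CP = 1 − Φ[(c − Z√t) / √(1 − t)] = 1 − Φ(1.2816/0.7071) = 1 − Φ(1.8124) = **3.496%**.

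At Z = 0 the observed hazard ratio is 1, so conditional power under the null and under the current trend coincide.

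**Step 4: could another reading give 3.5%?**

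| Change from the stated inputs | Predictive probability at the boundary |
|---|---|
| None | 10.0% |
| Binding futility, c = 1.250 | 10.6% |
| Unshifted boundary, Z = 0.116 | 13.2% |
| 44 events instead of 35 (t = 44/70) | 4.8% |
| One-sided alpha 0.05 | 5.0% |
| One-sided alpha 0.025 | 2.5% |

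None gives 3.5%. It would take about 67% information (about 47 of 70 events), which contradicts the 50% in both sections.

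For the prior, I assumed a normal prior centred on HR = 1 and worth n₀ events. The predictive variance of the final Z is then 0.5 × [1 + 35/(35 + n₀)].

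| n₀ | Variance | Predictive probability |
|---|---|---|
| 0 (flat) | 1.000 | 10.0% |
| 10 | 0.889 | 8.7% |
| 35 | 0.750 | 6.9% |
| 70 | 0.667 | 5.8% |
| → ∞ | 0.500 | 3.5% |

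Only a prior fixed at HR = 1 gives 3.5%, and that is the opposite of non-informative.

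**Step 5: where a 3.5% predictive probability would lie.** Setting PP = 0.035 gives Z = (1.2816 − 1.8119) × √0.5 = −0.375. The corresponding observed hazard ratio is exp(0.375 × 2/√35) = 1.14, not 1.

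**The case against.** The strongest reply is that Section 13.3 may describe a different look from Section 13.2. It times the interim by the 44th patient evaluable for response and interprets Z = 0 as equal response proportions, so the 3.5% might come from a binomial calculation. Its 0.116 also does not reproduce from the PFS design: beta-spending of that type at t = 0.5 with alpha 0.1 and beta 0.17 gives a non-binding boundary of about Z = 0.001. This suggests, without proving it, that the section's figures came from another calculation.

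The conflict between the sections is real, but it does not rescue the number. Section 13.3 itself states 50% information and Z = 0, and the trial's superiority test is the PFS logrank test at 0.1. Suppose instead a response comparison with 22 per arm at the interim, 44 per arm at the end, 0 to 8 responders in each arm at the interim, and Beta(0.5, 0.5) or Beta(1, 1) priors. With the Pearson chi-squared test that Section 13.5 names for response, the predictive probability runs from 8.3% to 13.3%. With a one-sided Fisher exact test it runs from 1.4% to 6.9%, which includes 3.5%, but the plan names no Fisher test.

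The second reply is that the figure does no operational work. That stands in part. The trigger is explicit and does not use 3.5%, enrolment is not suspended, and the power cost of the rule is already in the 83%. This limits the consequence but does not make the statement correct.

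**Conclusion.** The sentence is wrong as written. At Z = 0 and half the information, the flat-prior predictive probability of concluding superiority is 10.0%, so the plan understates it by a factor of 2.9 (10.0/3.5). The result rests on the normal approximation for the logrank Z, a flat prior on the log hazard ratio, and an unadjusted final critical value of 1.2816. The plan's own statements support the last two.

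That 3.5% is conditional power given the wrong name is an inference from a numerical match, because the documents do not show the calculation. The futility boundary, Type I error, sample size and 83% power do not change. It should be corrected because it misdescribes the only interim rule, but it does not threaten the primary analysis.

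**What to change.** Keep the boundary at Z = 0 and replace the sentence in Section 13.3 with: *At Z = 0 and 50% information, the Bayesian predictive probability of concluding superiority at the final analysis with a non-informative prior is 10%; conditional power under HR = 1 is 3.5%.*

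If the sponsor used a different prior, information fraction or final test, it should state it, because the present text cannot yield 3.5%. The new figure assumes the PFS look of Section 13.2, so the response wording in Section 13.3 should be brought into line when the sentence is edited. The correction of the figure costs one sentence and needs no change to the design or the analysis.
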